### 8.4.3. Pharmacokinetic Parameters and Evaluations

#### Parameters

Based on the individual plasma concentration-time data, using the actual dose taken and the actual sampling times, PK parameters ( $C_{\max}$ ,  $C_{\text{trough}}$  [trough concentration],  $AUC_{\tau}$ ) of BDQ at Day 1, Weeks 2, 8, 12, 24, and 48 will be derived using population PK modelling. If deemed necessary, a similar analysis for  $C_{\max}$ ,  $C_{\text{trough}}$ ,  $AUC_{\tau}$  will be performed for M2.

Baseline covariates (eg, body weight, age, sex) may be included in the model, if relevant.

The predose and 2 to 4 hours postdose plasma concentrations on Day 1, Weeks 2, 8, 12, 24, and 48 (for Week 48, BDQ and M2 only) of BDQ and M2 for Group A, and CAM and 4-OH CAM for both Group A and B will be listed.

#### Pharmacokinetic/Pharmacodynamic Evaluations

The relationship between BDQ (and CAM [optional]) PK and MAC-LD treatment outcome and safety endpoints may be evaluated as appropriate. Pharmacokinetics/pharmacodynamics analyses will be performed on the collected data when all participants have reached Week 24 or discontinued earlier. The PK/PD analyses may be performed at earlier time points as necessary to support efficacy and safety findings. If there is any visual trend in graphical analysis, suitable models will be applied to describe the PK/PD relationships. The results of the PK/PD evaluations will be presented in a separate report.

### 8.5. Genetics and Pharmacogenomics

Not applicable.

### 8.6. Biomarkers

Not applicable.

### 8.7. Immunogenicity Assessments

Not applicable.

### 8.8. Health Economics or Medical Resource Utilization and Health Economics

Not applicable.

## 9. STATISTICAL CONSIDERATIONS

Statistical analysis will be done by the sponsor or under the authority of the sponsor. A general description of the statistical methods to be used to analyze the efficacy and safety data is outlined below. Specific details will be provided in the Statistical Analysis Plan (SAP).

### 9.1. Statistical Hypothesis

The hypothesis of this study is that BDQ-containing regimen is superior to rifamycin-containing regimen and increases the proportion of participants with sputum culture conversion in MGIT at Week 24 as compared to the rifamycin-containing regimen.

## 9.2. Sample Size Determination

Based on the results of 2 clinical trials of ALIS (Phase 2 and Phase 3) in an analogous population, it is anticipated that the rifamycin-containing regimen in this study will have a sputum culture conversion rate assumed to be equal to 10% after 24 weeks of treatment.

A sample size of 124 participants (62 in Group A: the BDQ containing regimen, 62 in Group B: the rifamycin-containing regimen) will have a power of about 80% to show superiority for a 20% difference in proportion of participants having sputum conversion at Week 24 based on a chi-square test (at the 5% 2-sided significance level) on the intent-to-treat (ITT) population.

## 9.3. Populations for Analysis Sets

For purposes of analysis, the following populations are defined:

Population	Description
Enrolled	All participants who sign the ICF
Randomized	All participants who were randomized in the study.
Intent-to-treat (ITT)	All randomized participants who take at least 1 dose of study intervention. ITT will be the primary population for efficacy analyses.
Per-protocol (PP)	All ITT population with at least 3 consecutive sputum collections taken at least 25 days apart after baseline. Participants who have major protocol deviations will be excluded from the PP population. More details will be provided in the SAP.
Safety	All participants who take at least 1 dose of study intervention.
PK	All safety population with at least 1 PK measurement.

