### Blinding, Control, Study Phase/Periods, Treatment Groups

The Japanese guidelines currently recommend a 3-drug regimen, consisting of CAM, RFP or RBT, and EB, as SOC. The South Korean and Taiwanese guidelines recommend a 3-drug regimen consisting of macrolide (CAM or AZM), RFP or RBT, and EB as the SOC. Therefore, 3-drug regimen, consisting of CAM as macrolide is selected as control arm.

This study will be conducted by an open-label design. Because rifamycin, which is included in the control regimen, is known to cause a reddish coloration of the urine, feces, sputum, sweat, serum, and discoloration of soft contact lenses, blinding of the study drug/comparator is practically impossible due to the wide area of coloration effects. The primary endpoint at Week 24 is sputum culture conversion, which will be assessed based on the results of culture at the central microbiology laboratory. These microbiological results will be blinded to the investigator and

participants until the completion of the other assessments at Week 24. Randomization will be used to minimize bias in the assignment of participants to treatment groups, to increase the likelihood that known and unknown participant attributes (eg, demographic and baseline characteristics) are evenly balanced across treatment groups, and to enhance the validity of statistical comparisons across treatment groups.

The planned treatment duration of BDQ (48-week BDQ treatment period) is same as the maximum duration in the sponsor-conducted clinical study in Japanese participants with MDR-TB (Study TMC207TBC2001). Overall, the treatment success rate in treatment-refractory patients with the current treatment has been unsatisfactory and many patients remain culture positive despite prolonged therapy. The local guidelines for MAC-LD treatment in Japan, South Korea, Taiwan and an Official ATS/IDSA statement currently recommend treating until patients have been on SOC for 1 year after culture conversion, but there is no evidence to support this treatment duration.

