#### 4. POPULATIONS (ANALYSIS SETS) FOR ANALYSIS

Analysis Sets	Description
Enrolled	All participants who sign the ICF
Randomized	The randomized analysis set includes all participants who were randomized in the study. Participants will be analyzed according to the study intervention they were randomly assigned to.
Intent-to-treat (ITT)	All randomized participants who were randomly assigned to an intervention arm and who take at least 1 dose of study intervention. Participants will be analyzed according to the study intervention they were randomly assigned to. ITT will be the primary population for efficacy analyses.
Safety	The safety analysis set includes all participants who received at least 1 dose of the study intervention. Participants will be analyzed according to the study intervention they actually received.
Pharmacokinetics (PK) Analysis Set	The PK analysis set is defined as participants, regardless of their compliance with the protocol, who received at least 1 dose of the study intervention and have at least 1 valid blood sample drawn for PK analysis.
Pharmacokinetic/pharmacodynamic (PK/PD) Analysis Set	QTcF will be selected for safety parameter. MAC LD treatment outcome will be selected for efficacy parameter. The PK/PD analysis set includes all subjects who received at least 1 dose of BDQ and/or CAM, and have at least 1 time point with nominal time-matched plasma concentration and safety or efficacy parameter.

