## 5.2. Participant Dispositions

The number of participants in the following disposition categories will be summarized throughout the study by intervention group and overall:

- Participants randomized
- Participants who received study intervention
- Participants who completed the study
- Participants who discontinued study intervention
- Participants who discontinued study
- Participants who switched to the optional cohort

- Participants who switched to the individualized treatment regimen
- Reasons for discontinuation of study intervention
- Reasons for discontinuation of study

Listings of participants (eg, the date of last study visit, the last study phase and week, the date of discontinuation and the reason) will be provided for the following categories:

- Participants who discontinued study intervention
- Participants who discontinued study
- Participants who were randomized yet did not receive any study interventions.

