#### **5.3.2. Primary Estimand**

The main clinical quantity of interest to be estimated in this study, is defined by the following 5 components:

- Population: Adult patients with treatment-refractory MAC-LD
- Endpoint: Proportion of participants with sputum culture conversion (sputum culture conversion rate) in MGIT at Week 24.
- Treatment: BDQ-containing regimen versus rifamycin-containing regimen.
- Population Level Summary: The difference of proportions between treatment groups.
- Intercurrent Events (ICE):
  - a. Deaths, treatment discontinuation and treatment regimen changes prior to Week 24: all these ICEs will be handled by a composite strategy to treat the participants as nonconverters.
  - b. Major protocol deviations (besides treatment regimen changes prior to Week 24): all data will be used regardless of the occurrence of major protocol deviations (treatment policy strategy).

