### Data Included

All randomized participants who take at least 1 dose of study intervention will be used.

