### Data Included

Same as the main estimator.

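### The set called ITT contains dosed participants only, so in this open-label trial no planned efficacy analysis covers everyone randomised

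*Protocol*

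**What the plan says.** Protocol section 9.3 defines ITT as "All randomized participants who take at least 1 dose of study intervention. ITT will be the primary population for efficacy analyses". SAP section 4 has the same restriction: "All randomized participants who were randomly assigned to an intervention arm and who take at least 1 dose of study intervention".

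The SAP carries it through the analyses of the primary endpoint. For the main estimator (5.3.2.1), the data are "All randomized participants who take at least 1 dose of study intervention will be used". The sensitivity estimator (5.3.2.2) is "Same as the main estimator". The supplementary estimand (5.3.3.1) repeats the dosed-only wording.

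Both documents also define a Randomized set, but neither assigns it an efficacy analysis. SAP Appendix 2 lists one change to the protocol's analyses, the removal of the per-protocol set, so it does not alter this. Undosed participants appear only in SAP 5.2, through the disposition counts and a listing of "Participants who were randomized yet did not receive any study interventions".

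Two other provisions matter here. Protocol section 4.2 states: "This study will be conducted by an open-label design". For deaths, treatment discontinuation and regimen changes before Week 24, SAP 5.3.2 states: "all these ICEs will be handled by a composite strategy to treat the participants as nonconverters".

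**The concern.** Intention-to-treat analysis protects the randomised comparison because nothing after allocation decides who is counted. Here the first dose does. In a double-blind trial that condition is usually harmless, because failure to start cannot depend on a known assignment. In this trial the participant and the investigator know the arm. Central culture reading, with results blinded to Week 24, protects the assessment of the outcome but not the make-up of the denominator.

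The treatment of failures is also uneven. Someone who stops after a single dose counts as a non-converter, while someone who withdraws just before it leaves the analysis. The population named in the primary estimand is adults with treatment-refractory MAC-LD, not those who accepted a first dose. At stake is whether the primary superiority test rests on the full randomised comparison.

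**Working it through.** **Inputs.** Protocol 9.2 and SAP 3 give 62 per arm, 10% conversion in Group B, a 20-point difference (so 30% in Group A), and a two-sided 5% chi-square test. The documents give no number of undosed participants; 0 to 5 per arm is assumed.

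**1. The plan's own figure.** With pooled proportion 0.20, the null standard error is √(0.20 × 0.80 × 2/62) = 0.0718. The alternative standard error is √(0.30 × 0.70/62 + 0.10 × 0.90/62) = 0.0696. Then (0.20 − 1.96 × 0.0718)/0.0696 = 0.851, which gives power of 80.3%. The stated figure of about 80% reproduces. It takes 62 analysed per arm, with no stated allowance for undosed participants.

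**2. Shift at the planned rates.** The nearest whole counts are 19/62 in Group A and 6/62 in Group B. Undosed participants are taken to be non-converters, so the dosed-only set shrinks the denominator and leaves the numerator alone. The p-values are from an unstratified, uncorrected chi-square, as an illustration; the planned test is Cochran-Mantel-Haenszel by region.

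| Dropped | Group A | Group B | p |
|---|---|---|---|
| None | 19/62 = 30.6% | 6/62 = 9.7% | 0.0036 |
| 3 from A | 19/59 = 32.2% | 6/62 = 9.7% | 0.0022 |
| 5 from A | 19/57 = 33.3% | 6/62 = 9.7% | 0.0016 |
| 3 from B | 19/62 = 30.6% | 6/59 = 10.2% | 0.0054 |
| 5 from B | 19/62 = 30.6% | 6/57 = 10.5% | 0.0071 |

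The largest movement in an arm is 33.3 − 30.6 = 2.7 points. Every p-value stays well below 0.05.

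**3. Borderline results.** With the same test:

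- 14/62 v 6/62 gives p = 0.0508. Dropping one undosed Group A participant, 14/61 v 6/62, gives p = 0.0461.
- 15/62 v 6/62 gives p = 0.0312. Dropping five from Group B, 15/62 v 6/57, gives p = 0.0507.

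The exclusion can therefore push the result in either direction.

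**4. Power under the two approaches.** The dosed are assumed to convert at 30% and 10%. For the all-randomised analysis, each arm's rate is multiplied by the dosed fraction. Three undosed in Group A, for example, gives 0.30 × 59/62 = 28.5%, a difference of 18.5 points.

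| Undosed | All randomised | Dosed only |
|---|---|---|
| 0 | 80.3% | 80.3% |
| 3 per arm | 77.7% | 78.2% |
| 3 in A only | 75.1% | 79.4% |
| 3 in B only | 82.5% | 79.1% |

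**The case against.** The best case on the other side is that the set of excluded participants may be empty.

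- The schedule of activities puts randomisation and first dose on Day 1, which leaves little time to withdraw.
- Group B non-converters may move to the bedaquiline regimen after Week 24 (protocol 4.1 and 6.8.2), which weakens the motive to refuse the control arm.
- The SAP version 4 history drops an estimand on the ground that all subjects met the 80% compliance threshold. By the Appendix 7 formula a never-dosed participant would score 0%. If the statement covers everyone randomised, nobody was undosed. It may cover dosed subjects only, and the text does not say which.

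These points stand as limits on size. They do not give the plan an all-randomised analysis. Where the SAP says results are summarised as randomised, that governs the arm a participant is counted in, not who is included.

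It is also fair to say that the two documents agree with each other, and that a person who never started has not, strictly, discontinued. So this is a choice of set and label rather than a contradiction. Disposition counts by arm would make any exclusion visible, although they would not repair the comparison.

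Some stronger readings are tempting but are not supported:

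- **QT monitoring as a deterrent specific to Group A.** ECGs are scheduled at every visit for both arms, and protocol 2.3.1 attributes the QT risk to bedaquiline and/or clarithromycin, which both arms take.
- **The listing in SAP 5.2 as a sign that undosed cases are expected.** It is one disposition listing among several and predicts no number.
- **A bias towards bedaquiline.** Loss from Group B would work against it.

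**Conclusion.** The point holds as a defect of definition with a probably small effect. Every planned analysis of the primary endpoint uses a dosed-only set under the name ITT, and the trial is open-label, so exclusion before the first dose can depend on the arm. The documents do not show that any such exclusion occurred, or in which arm.

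At the planned rates, and with at most 5 undosed in one arm, the conclusion does not change. A change needs a borderline result. This rests on the assumed 0 to 5 range, on treating undosed participants as non-converters, and on an unstratified test in place of the planned stratified one. The case for changing is that the remedy is cheap and gives identical results if nobody was undosed.

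**What to change.** - Run the primary Cochran-Mantel-Haenszel test and the stratum-adjusted difference on the existing Randomized set, by assigned arm, with undosed participants as non-converters. This extends the composite strategy already in SAP 5.3.2.
- Relabel the present set modified ITT and keep it as a sensitivity analysis.
- Report undosed participants by arm with reasons.
- Leave the Safety set unchanged.

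The cost is wording in protocol 9.3 and SAP 4, 5.3.2.1 and 5.3.3.1, with no new data. If anyone was undosed, conversion rates fall slightly, and power falls if they are in Group A (75.1% against 79.4% with three there). Anyone randomised who then lost eligibility before dosing (schedule of activities, footnote h) would count as a non-converter, so the report of reasons should identify them.

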## 9.4. Statistical Analyses

The SAP will be finalized prior to DBL and it will include a more technical and detailed description of the statistical analyses described in this section. This section is a summary of the planned statistical analyses of the most important endpoints including primary and key secondary endpoints.

### 9.4.1. General Considerations

All efficacy and safety data will be summarized by treatment groups (Groups A and B). For the Group B, data from optional cohort will be analyzed separately.

### 9.4.2. Primary Estimand

The primary estimand, the main clinical quantity of interest to be estimated in this study, is defined by the following 5 components:

- Population: Adult patients with treatment-refractory MAC-LD.
- Endpoint: Proportion of participants with sputum culture conversion in MGIT at Week 24.
- Treatment: BDQ-containing regimen versus rifamycin-containing regimen.
- Intercurrent Events (ICE):
  - a. Deaths, treatment discontinuation and treatment regimen changes prior to Week 24: all the ICEs will be handled by a composite strategy to treat the participants as non-convertors.

- b. Major protocol deviations: all data will be used regardless of the occurrence of major protocol deviations (treatment policy strategy).
- Population Level Summary: The difference of proportions between treatment groups.

### 9.4.3. Primary Endpoint

Sputum Culture Conversion in MGIT at Week 24.

The Cochran-Mantel-Haenszel test stratified by region (Japan, non-Japan) at the 5% 2-sided significance level will be used to compare sputum culture conversion rate in MGIT at Week 24. Participants with missing sputum samples that impact the ability to assess sputum culture conversion (ie, 3 consecutive negative sputum cultures taken at least 25 days apart) will be imputed as non-convertors in the analysis. Participants requiring a treatment regimen change to individualized regimen will also be considered as non-convertors. A contaminated sputum culture or failed culture occurring between two negative cultures will be interpreted as “no data”, and will be ignored for the assessment of the 3 consecutive negative cultures. More details will be provided in the SAP. Subgroup analyses will be performed for important baseline disease characteristics.

### 9.4.4. Secondary Endpoints

- Sputum culture conversion in MGIT and 7H10 or 7H11 agar media (other than MGIT at Week 24).

The percentage of participants with sputum culture conversion (defined as 3 consecutive negative sputum cultures taken at least 25 days apart) in MGIT and 7H10 or 7H11 agar media will be calculated after Week 4. The percentage of participants who achieved sputum culture conversion at Week 24 and completed 48-week BDQ-containing regimen and achieved sputum culture conversion at Week 60 in Group A will be compared with the percentage of participants who completed 60-week SOC regimen and achieved sputum culture conversion at Week 60 in Group B using the Cochran-Mantel-Haenszel test stratified by region (Japan, non-Japan).

- Sputum culture negativity in MGIT and 7H10 or 7H11 agar media.

The percentage of participants with sputum culture negativity in MGIT and 7H10 or 7H11 agar media will be calculated at each visit after Week 2, respectively. A generalized linear model including treatment, region (Japan, non-Japan), time, and treatment-by-time interaction as fixed effects will be applied for the number of negative culture participants and the number of all participants at each timepoint and comparison between treatment groups will be performed using the appropriate contrast for the percentage of negative culture participants at Week 24.

- Time to sputum culture conversion in MGIT.

Time to sputum culture conversion in MGIT is calculated as the interval in days between the initiation date of the study intervention and the sampling date of the first of the 3 consecutive negative sputum cultures from sputum samples collected at least 25 days apart. Kaplan-Meier estimates will be generated for the time to sputum culture conversion up to Week 24 and Week 48. The difference between the treatment groups will be compared using the log-rank test stratified by region (Japan, non-Japan) for the time to sputum culture conversion up to Week 24. For

participants with no sputum culture conversion during the analysed period, time to culture conversion is censored on the last assessment day of the analysed period.

- Time to positivity in MGIT.

Time to positivity is calculated as the time required to positive signal in MGIT. A recent study showed a similar correlation between CFU and time to positivity with MAC.

- SGRQ.

The changes from baseline in total score of SGRQ and domain scores will be summarized descriptively at Weeks 24, 48, and 60. For the total score of SGRQ at Week 24, the difference in the change from baseline between the treatment groups will be provided using an analysis of covariance (ANCOVA) model.

- Percentage of participants who undergo a change in their MAC-LD treatment regimen.

The percentage of participants who are changed from randomized treatment regimen to the individualized treatment regimen, including switched to the optional cohort is calculated.

